5.2 Treatment Procedures

5.2.1 Selection of Study Population

For the phase II trial, potential research participants with active cryptococcal meningitis will be identified by active surveillance during hospitalization by the on-site study teams and consented for screening. Secondary surveillance will be via the site microbiology laboratories with study team notification of new positive culture or CrAg results.

5.2.2 Timing of Study Enrollment

For the phase II trial, potential participants would be determined as eligible after lumbar puncture results. The diagnostic lumbar puncture is considered a routine medical procedure; with meningitis considered a medical emergency. Participants can be enrolled anytime in the first 2 days of 5-FC therapy. This allows time for informed consent without any undue, coercive time pressure. Receipt of >2 days of 5-FC therapy is an exclusion.

5.3 Informed Consent Process

5.3.1 Study Screening and Storage Consent

Since serum and CSF will be stored, consent for specimen storage and data collection will be obtained at the time of the initial diagnostic lumbar puncture (when the cryptococcal meningitis diagnosis is unconfirmed) prior to obtaining consent for the main overall trial. A screening and storage consent (or surrogate consent from caregiver/next of kin) will be required for study personnel to perform a lumbar puncture (LP) screening for CM diagnosis to verify an inclusion criterion. Persons with altered mental status are eligible for screening diagnostic lumbar

puncture for meningitis diagnosis with surrogate consent, even if they are not eligible for the overall study (as it would be unethical to withhold appropriate diagnostics from critically ill patients). This screening and storage consent requests to “record information about their current illness,” including presenting symptoms (assessed prior to LP), final diagnosis (based on CSF results and physician diagnosis), and vital status at hospital discharge.

This screening /storage consent may be via this or another research study (e.g., EnACT) in order to make the diagnosis of cryptococcal meningitis and assess for this trial’s eligibility criteria. If persons are referred from outside health care facilities with documentation of CM per study inclusion criteria, they will be eligible; however, these persons must have an LP with a full diagnostic CSF analysis performed after study screening consent and prior to entry into the study to confirm the diagnosis and exclude alternative diagnoses.

As meningitis is a medical emergency, after the diagnosis of cryptococcal meningitis is confirmed, persons start on standard IV AMB and 5-FC therapy. The first dose of 5-FC is study day 1.

5.3.2 Informed Consent

Informed consent is a process that is initiated prior to the individual agreeing to participate in the study and continuing throughout the individual’s study participation. After CM diagnosis and eligibility criteria are confirmed, informed consent will be obtained by a study investigator who will provide potential subjects with an IRB approved consent form in English or Luganda (Kampala) or Runyankole (Mbarara). Informed consent must occur prior to participants receiving 12 or more doses of 5-FC. There is a window of time to allow for informed consent process without any undue, coercive time pressure or unethical withholding of antifungal therapy until consent is provided. Participants may have received fluconazole and remain eligible. However, potential participants will be given appropriate time to consider the study. At the time of informed consent, a complete history and physical examination will be performed to verify inclusion/exclusion criteria.

During the Informed Consent process, the investigator will describe the purpose, risks, and benefits related to the study. Each aspect of the forms will be explained in detail with the potential subject, and the potential subject will have the opportunity to ask any questions regarding the study. The investigator obtaining informed consent will ask questions to assess the subject’s understanding. The investigator will state that participation is voluntary and that subjects may refuse participation or withdraw at any time without prejudice to their clinical care. Persons who decline participation will continue the same CM induction therapy according to current standards of care.

Since this study may require additional blood draws beyond the standard of care, additional consent will be required from subjects receiving blood draws for stored samples for future study purposes. In this case, samples will be stored indefinitely, unless the subject has a change of mind and asks for them to be destroyed.

Specimens do need to be collected as pharmacokinetics is a key component of the study.

If, in the opinion of the investigator, potential participants who do not have appropriate comprehension, the investigator must re-explain the study or determine whether the participant's current mental capacity is diminished due to the CM and pursue surrogate consent.

Consent for Lumbar Punctures: Lumbar punctures will be explained in detail in the meningitis screening sample storage consent and main trial informed consent form. All follow up therapeutic LPs are deemed standard of care to control intracranial pressure and document clearance of infection. Participants retain the right to refuse a follow up LP, although this is not recommended as therapeutic LPs have a strong survival benefit. One follow up therapeutic LP is associated with a 69% relative survival benefit in the first ~10 days.⁵² A second therapeutic LP in the second week has a 50% reduction in 30-day mortality (33% vs 22%) in Uganda.⁵⁵ Refer to Section 8.2 for the recommended LP schedule.

Storage Consent: Informed consent for long-term storage of samples for future research testing is necessary by Ugandan regulations. This will be completed according to the COAST protocol which is a parallel study into which all FLOOR participants will be enrolled. Refer to Section 12.6 for further details.

5.3.3 Capacity to Consent

Assessment of the capacity to consent is required for all participants in the study that have a GCS of 15. The UCSD Brief Assessment of Capacity to Consent (UBACC) will be administered to all subjects. The UBACC is an adapted, validated tool consisting of 10 questions worth 3 points each for assessing the capacity to consent in clinical trials.⁵⁶ If GCS is 15, then UBACC will be administered to assess capacity to consent. If the subject scores 15 or better on the assessment, then they can self-consent. **A GCS of <15 or UBACC assessment score of <15 means that the individual does not have the capacity to consent.** Documentation that the assessment was administered and completed will be included in the study file.

5.3.4 Surrogate/Proxy Consent

Subjects who are unable to give informed consent due to the lack of capacity to consent or other barrier may enroll in the study with surrogate consent.

5.3.5 Literacy

A person who speaks and understands the language of the informed consent document, but does not read and write, can be enrolled in a study by "making their mark" via a thumbprint on the informed consent document.

In this event, an impartial, literate third party must witness the entire consent process and sign the informed consent document. The witness's name, signature, and relationship must be recorded on the informed consent document. A member of the study team is not an impartial third party.

5.3.6 Waiver of Informed Consent

CrAg LFA screening by fingerstick, serum, and/or plasma is to be performed as routine diagnostic care (without written informed consent) due to the high prevalence of CrAg+ individuals hospitalized. At Mulago Hospital in Kampala, Uganda in 2010, the prevalence of

CrAg+ individuals with CD4<100 was 21% on the infectious disease ward.⁵⁷ In Uganda, this point-of-care CrAg testing has been standard of care to rapidly identify persons with disseminated cryptococcal infection.

5.4 Blinding

This study will be a single arm phase II trial. Study medications will be dispensed by a study pharmacist of record.

5.5 Premature Discontinuation of the Intervention

A study subject can discontinue the study intervention (low-dose 5-FC) in the event of any of the following:

- Any clinical adverse event (AE), laboratory abnormality, concurrent illness, or other medical condition or situation occurs such that continued participation with an intervention would not be in the best interest of the subject
- Decompensation of the cryptococcal meningitis
- Subject wishes to voluntarily discontinue therapy

Subjects are free to discontinue an intervention at any time upon request or in the opinion of the investigator in the event of decompensation and disease progression. Examples of progression would be development of altered mental status, increasing CSF quantitative culture CFU counts by >1 log₁₀ CFU/mL, other medical events leading to an inability to take oral medicines, etc.

Subjects discontinuing low-dose 5-FC would then be given standard dose 5-FC, as clinically necessary.

Every effort will be made to undertake protocol-specific study procedures. If voluntary discontinuation occurs, the subject will be asked to continue scheduled evaluations, complete an end-of-study evaluation, and be given appropriate care under medical supervision until the symptoms of any AE resolve or the subject's condition becomes stable. The patient will be offered ongoing follow-up care at the site outpatient HIV clinic or referred to a clinic of their choice if withdrawn from the study.

Alterations in dose will be considered a protocol deviation, since the goal of the trial is to assess the effect of dose-reduction. Patients may remain in the study but dose-adjustments will be documented and reported to the IRB.

Subjects discontinuing the intervention will receive standard of care therapy through 18 weeks.

5.6 Study Withdrawal

By consenting to the trial, participants are consenting to receiving the study treatment, study follow-up and study data collection. However, a study subject may discontinue from further ongoing study participation at any time if:

- Subject wishes to voluntarily withdraw.
- Fulfillment of early withdrawal criterion: absolute neutrophil count < 500 x 10⁶ cells/L, thrombocytopenia < 50,000 x10⁶ cells/L, or renal creatinine clearance < 20 mL/minute

- Any unacceptable toxicity or adverse event (ie. Development of severe renal dysfunction or leukopenia on treatment).

Subjects are free to withdraw from participating in the study at any time upon request. If voluntary withdrawal occurs, the subject will be asked to complete an end-of-study evaluation and be given appropriate care under medical supervision until the symptoms of any AE resolve or the subject's condition becomes stable. The patient will be offered ongoing follow-up care at the site outpatient HIV clinic or referred to a clinic of their choice if withdrawn from the study. Participants who withdraw from Mulago hospital will not be contacted after withdrawal of consent.

Subjects may discontinue the study intervention (as per Section 5.5) and remain in the research study for safety monitoring and assessment of endpoints, receiving standard of care therapy.

Subjects withdrawing from the study will be recommended to receive standard of care therapy.

6. MEDICATIONS TO BE USED IN THE TRIAL

With the exception of the intervention of low-dose 5-FC, all medications received in this study are considered standard of care and will be provided by the study. HIV antiretroviral medicines will not be provided by the study but are freely available, regardless of study population, via the public sector HIV clinics.

6.1 Cryptococcal Meningitis Management

Medication management is summarized in Table 6.2, as per 2018 and 2022 cryptococcal WHO guidelines,^{4,58} which exceed the local standard of care.

Table 6.2: 2018 and 2022 WHO Treatment Regimen for Cryptococcal Meningitis

Medication and Dose	Week 1	Week 2	Week 3-10	Week >10
Amphotericin B (1.0 mg/kg/day) + flucytosine 100mg/kg/day ^a				
Fluconazole 1200mg daily				
Fluconazole 800mg daily				
Fluconazole 200mg daily				Through 12 months
Treatment Phase	Induction	Induction	Consolidation	Secondary Prophylaxis

Notes: ^a Flucytosine (5FC) 100 mg/kg/day preferred where available, otherwise fluconazole at 800–1200mg/day in divided doses with two weeks of amphotericin B. KCl 40–60 mEq/day should be given with amphotericin.

Individual patient factors often alter patient care and fluconazole dosage on an individual basis at physician discretion, such as acute renal failure, duration of cryptococcal culture positivity, CM relapse, medication intolerance, and hepatic P450 drug-drug interactions (e.g. rifamycin).

As well, some individuals will remain CSF culture positive after 14 days of amphotericin, thus higher dose fluconazole with fungicidal activity (1200 mg/day) may be used until outpatient clinic enrollment at Study Week 4. For persons with persistently positive cultures, refer to Section 7.4 on outpatient clinical management of CM. Induction therapy using a combination of amphotericin and either high-dose fluconazole or flucytosine is recommended as the microbiologic activity is greater than that of amphotericin alone. Subjects who remain CSF culture positive should continue on at least induction-dose fluconazole until culture negative.

6.2 Other Antifungals Used in Cryptococcal Treatment

6.2.1 Amphotericin B

Amphotericin B is an antifungal polyene. Amphotericin is well known for its frequent and potentially severe side effects. For this reason, it is used only for the treatment of life-threatening fungal disease, such as CM, where it may be the only effective treatment available. In all cases, possible life-saving benefits of amphotericin must be balanced against its untoward and dangerous side effects.

6.2.1.1 Amphotericin B Deoxycholate

Amphotericin B deoxycholate is available in single vials. Each vial contains a sterile, non-pyrogenic, lyophilized cake providing 50 mg amphotericin B and 41 mg sodium deoxycholate buffered with sodium phosphates. Amphotericin B is solubilized by the addition of sodium deoxycholate to form a mixture, which provides a colloidal dispersion for intravenous infusion following reconstitution.

Typical AMB deoxycholate dosing for CM is 0.7-1 mg/kg daily. Amphotericin should be administered by slow intravenous infusion over a period of approximately 4 hours. The recommended concentration for intravenous infusion is 0.1 mg/mL (1 mg/10 mL).

Acquisition: Any nationally registered, GMP-manufactured, and/or FDA-approved formulation is acceptable.

Product Storage and Stability: Prior to reconstitution, AMB deoxycholate should be stored under refrigeration 2° to 8°C (36° to 46°F) and protected against exposure to light.

Study administration for all treatment arms:

Subjects will receive the WHO standard 7-day course of IV amphotericin B deoxycholate 0.7-1.0mg/kg/day.

Amphotericin is well known for its frequent and often severe side effects, as outlined in Appendix A. Significant infusion reactions must be anticipated with a tendency toward IV-associated phlebitis. To help prevent this, IV lines will be flushed after amphotericin is administered and peripheral IV sites generally rotated at least every 3 days. With IV AMB, provide 1–2 L saline/day, along with careful monitoring for renal dysfunction and particularly electrolyte abnormalities (K and Mg). Electrolyte management with amphotericin is essential, and will follow WHO treatment guidelines including supplemental potassium and magnesium.⁵³

Guidelines for use of IV AMB and management of common toxicities associated with amphotericin B are included in the MOP and may be consulted, at the site investigator's discretion. Participants who permanently and prematurely discontinue IV AMB because of an AE will be followed closely until resolution of the AE can be documented. Those who require additional IV AMB in any arm will be tracked, as additional IV AMB is a secondary endpoint.

When not receiving IV AMB, additional IV fluids will be given as clinically indicated.

6.2.1.2 Liposomal Amphotericin B

Liposomal amphotericin B (AmBisome®), Gilead, Inc. is dosed at 10 mg/kg/dose in a single dose.

Acquisition: Liposomal preparations of amphotericin B are rarely available in Africa, but may be more so in the future. AmBisome® may be substituted for AMB deoxycholate depending on availability.

Product Storage and Stability:

Liposomal amphotericin B may be stored at temperatures up to 25°C.

Study Administration:

Subjects will receive the WHO revised standard single high dose liposomal Amphotericin B 10 mg/kg/dose.⁴ Liposomal amphotericin will be the preferred regimen when available to the study team. If liposomal Amphotericin is not available then Amphotericin deoxycholate will be used.

The same guidelines for use of IV AMB and management of its toxicities as described above in Section 6.2.1.1. will be followed.

6.2.2 Flucytosine

Flucytosine (5-fluorocytosine) is a fluorinated pyrimidine that is available as 250mg and 500mg oral capsules. Flucytosine is a white crystalline powder and the following inactive ingredients: cornstarch, lactose, and talc.

Typical dosing is 100mg/kg/day divided in 6-hour intervals. Flucytosine is rapidly and virtually completely absorbed following oral administration.

Flucytosine is taken up by fungal organisms via the enzyme cytosine permease. Inside the fungal cell, flucytosine is rapidly converted to fluorouracil (5-FU) by the enzyme cytosine deaminase. Fluorouracil exerts its antifungal activity through the subsequent conversion into several active metabolites, which inhibit protein synthesis by being falsely incorporated into fungal RNA or interfere with the biosynthesis of fungal DNA through the inhibition of the enzyme thymidylate synthetase.

Acquisition: Any GMP-manufactured Flucytosine is acceptable.

[figure not shown]
Product Storage: Flucytosine should be stored at room temperature between 15-30°C.

Study administration:

Investigational cohort: Subjects enrolled will receive 10 days of flucytosine at 60mg/kg/day in 3 divided doses. Three divided doses are a general recommendation. Based on the number of tablets or GI tolerability, the number of doses can be altered. Table 6.2.2 provides an example approximate dosing schedule.

Table 6.2.2 Example Daily Dosing Regimen by Weight

Weight	Total 500mg Tablets Per Day	Pills per Dose	Mg/Kg Dose Range
<30	Weight based dosing	Respective pills every 8 hours	
30-38	4	2, 1, 1	54.1 - 66.7
38-44	5	2, 2, 1	56.8-65.8
45-53	6	2, 2, 2	55.6-66.7
54-62	7	3, 2, 2	56.2 - 64.8
63-70	8	3, 3, 2	57.5 - 63.5
71-79	9	3, 3, 3	57.0 - 63.4
80-87	10	4, 3, 3	57.5 - 62.5

88-94	11	4, 4, 3	58.5 - 62.5
95-103	12	4, 4, 4	58.3 - 63.2
>104	Weight based dosing		

Estimated weight is acceptable to use (e.g. in comatose or confused persons unable to stand on a scale). Dose should be adjusted once a measured weight is available. There is a general preference to round up when between weight bands or when in doubt.

Cautions. Flucytosine must be given with extreme caution to patients with impaired renal function or bone marrow depression. Since flucytosine is excreted primarily by the kidneys, renal impairment may lead to accumulation of the drug. Flucytosine serum concentrations should be monitored to determine the adequacy of renal excretion in such patients. Dosage adjustments should be made in patients with renal insufficiency to prevent progressive accumulation of active drug. Patients may be more prone to depression of bone marrow function if they: 1) have a hematologic disease, 2) are being treated with radiation or drugs which depress bone marrow, or 3) have a history of treatment with such drugs or radiation. Bone marrow toxicity can be irreversible and can lead to death. Frequent monitoring of hepatic function and of hematopoietic system is indicated during therapy.

Side Effects. Other common side effects include headache, rash, nausea, vomiting, diarrhea, and abdominal pain. The potential side effects will be discussed with patients at study entry, with close monitoring for adverse events.

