The combination of amphotericin and flucytosine appears to be rapidly fungicidal and has better survival than alternative 14-day regimens.^{2,29-31} Flucytosine can also be associated with severe side effects including hepatotoxicity, bone-marrow depression, and renal toxicity when co-administered with other nephrotoxic drugs such as amphotericin.³² Furthermore, flucytosine is currently not registered or available in most low and middle income countries. Given the apparent advantages of flucytosine over fluconazole as combination therapy, substantial advocacy efforts are currently underway to secure availability and affordability of flucytosine where *Cryptococcus* is prevalent. In 2019, UNITAID was seeking to make flucytosine available.

In contrast to amphotericin, fluconazole is generally well-tolerated and readily penetrates the central nervous system (CNS).³³ Consolidation and subsequent maintenance therapy therefore relies on extended courses of oral fluconazole (Table 2.3). At typical doses (≤ 400 mg/day),

however, fluconazole is fungistatic rather than fungicidal, confirmed in a well-designed clinical trial demonstrating no change in fungal growth by serial quantitative cultures over 2 weeks with 400 mg/day of fluconazole.²⁶ Even when used in higher, more fungicidal doses (800-1200 mg/day)¹⁹ as is currently being recommended for induction therapy of CM, fluconazole adds a marginal contribution to overall fungal clearance when used together with amphotericin. Fluconazole monotherapy, which is still the standard of care in much of the world where amphotericin use is limited or impossible to administer, leads to suboptimal clearance, resistance and symptomatic relapse.^{34,35} More efficacious and less toxic oral antifungals for the treatment of cryptococcosis are urgently needed.

[figure not shown]

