2.6 Potential Risks and Benefits

2.6.1 Potential Risks

First, the EFA, which as described above, indicates the rate of fungal clearance and correlates with mortality due to CM will be followed by the study team. If EFA is consistently $<0.2 \log_{10}$ CFU/mL/day after 10 enrolled patients, then the trial will be suspended until an interim review

can be completed. In addition, all patients will be receiving IV AMB which is also a gold standard therapy and reduces mortality related to CM, in addition to fluconazole.

As discussed above 5-FC is a critical aspect of the induction phase of treatment for CM, decreasing the fungal burden in the CNS and improving mortality. Given this, there is a risk that decreasing the dose of 5-FC will lead to insufficient CSF concentrations to achieve fungal clearance and reduced mortality. For this reason, we will implement several safety measures.

As discussed above, our trial will use the induction therapy regimen established in the AMBITION-cm trial and now recommended by the updated WHO guidelines.⁴ During phase 2 of that trial, high dose liposomal Amphotericin B with fluconazole achieved an EFA of $-0.52 \log_{10}$ CFU/mL/day.³⁸ These data provide strong evidence that optimizing the dose of 5-FC can be safely studied in the same context without significantly reducing mortality.

The risks associated with the traditional IV AMB include nephrotoxicity, life-threatening hypokalemia (common), life-threatening hypomagnesemia (common), severe anemia (common), nausea (common), vomiting (common), diarrhea (common), severe infusion reactions including rigors, local inflammation, and thrombophlebitis (common), and many other less common side effects.

Amphotericin B is an FDA pregnancy category B (no evidence of risk in humans); however, all participants will also receive flucytosine and fluconazole, which are both potential teratogens at high doses. Therefore, subjects must use effective forms of contraception to avoid becoming pregnant. Pregnant women will be excluded.

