3.2 Study Outcome Measures

Primary Endpoint

1. CSF culture clearance at 2 weeks (Early Fungicidal Activity, or EFA: change of \log_{10} *Cryptococcus* CFU/mL CSF/day as measured by serial quantitative CSF fungal cultures)

Key Secondary Endpoint

1. Desirability of Outcome Response (DOOR) as ordinal ranked maximum score tested by Win Ratio.
 - a. 18-week Survival with CSF sterility by 2-weeks
 - b. 18-week survival with CSF culture positivity beyond 2 weeks
 - c. Grade 3 hematological adverse event by 2 weeks
 - d. Grade 4 hematological adverse event by 2 weeks
 - e. Lost to follow up before 18-weeks
 - f. Serious Adverse Event through 18 weeks (e.g. all-cause re-hospitalization, permanent neurologic deficit)
 - g. Death by 18-weeks

Secondary Endpoints

1. CSF culture sterility cumulative incidence over 18 weeks
2. 18-week survival time

[figure not shown]
Safety & Exploratory Endpoints

1. Incidence of Grade 3-5 abnormal laboratory test results (as per the NIAID DAIDS toxicity grading scale) through Week 2 of the study
2. Incidence of clinical Adverse Events (Grade 3-5) or SAEs through week 2
3. Pharmacokinetics of 5-FC concentrations in blood, CSF, and other tissues.

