4. STUDY DESIGN

4.1 Phase II Study Design

Figure 4.1

This is a single-arm trial with historical controls to compare the efficacy and safety of reduced dosing of 5-FC induction therapy for the treatment of cryptococcal meningitis in combination with IV AMB to standard of care, with EFA as the primary endpoint.

Participants will be enrolled into an investigational cohort at study entry.

1. The investigational cohort will receive 60mg/kg/day of 5-FC divided into 3 doses per day for 10 days, n~50 total enrolled to achieve n=36 CSF culture positive.
2. The control group will consist of historical participants in the AMBITION trial
3. All participants will receive liposomal Amphotericin B 10 mg/kg, single-dose infusion, if available.
4. If liposomal Amphotericin is unavailable, participants will receive IV amphotericin deoxycholate 0.7-1.0 mg/kg/day for 7 days.
5. All participants will receive fluconazole 1200 mg/day during induction therapy from day 1 to 14 then consolidation therapy 800 mg/day from day 15 to 10 weeks, and maintenance therapy of 200 mg/day after 10 weeks.
6. All participants will receive lumbar punctures at diagnosis, day 3, day 5-7, day 10-14, and additionally as required for control of intracranial pressure and documentation of CSF sterilization. Therapeutic LPs conducted during the first week have a ~70% relative survival benefit.

Investigational cohort will receive:

- IV Amphotericin B deoxycholate 1 mg/kg/day for 7 days or IV Liposomal Amphotericin B 10mg/kg single dose.
- Oral flucytosine (5FC) 60mg/kg/day for 10 days in 3 divided doses
- Oral fluconazole 1200mg/day from Day 1 to 14
- Oral fluconazole 800mg/day from Day 15 to Week 10
- Oral fluconazole 200mg/day thereafter

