At the Week 6 visit, a medical officer will assess:

- Interval history
- Review of medications and adherence
- Focused physical and neurologic exam, directed by symptoms
- Laboratory evaluation:
 - Complete blood count (CBC)
 - Serum sodium, potassium, creatinine
 - ALT, AST, T-bilirubin, alkaline phosphatase
 - Lumbar puncture if Week 4 is not sterile
 - Storage of leftover plasma and serum for pharmacokinetic / immunology studies
- Consider ART initiation (or switch to second line ART) if clinically stable
- Week 6 is the end of the collection period for expedited SAE reporting as all care afterward is the observational standard of care therapy.
- A lumbar puncture will be repeated only if the most recent CSF analysis is culture positive at time of visit.

Week 8 Outpatient Study Visit

Routine HIV care is provided.

- Any clinically significant (i.e. symptomatic) laboratory abnormality should be considered for follow up.
- A lumbar puncture will be repeated only if the most recent CSF analysis is culture positive at time of visit.

Week 10 Outpatient Study Visit

At the Week 10 visit, a medical officer will assess:

- Interval history
- Review of medications and adherence
- Focused physical and neurologic exam, directed by symptoms
- Laboratory evaluation follow up of unresolved AEs
- Lumbar puncture will be repeated if no prior sterile culture has occurred.
- Change to Fluconazole 200mg/day secondary prophylaxis; unless there is a reason to continue higher dose fluconazole (history of CM relapse, CM-IRIS, concurrent fungal infection, or other reasons per medical officer clinical judgment), according to current guidelines for long-term secondary prophylaxis.⁴

Week 12 Outpatient Study Visit

At the Week 12 visit, a medical officer will assess:

- Interval history
- Review of medications and adherence
- Focused physical and neurologic exam, directed by symptoms
- Evaluation of quantitative neurocognitive function at 12 weeks.⁶⁰

Commented [1]: Should move to week 12 to align with coast

Week 18 Termination Visit

Week 18 is the final scheduled visit of the study. This visit can be conducted by phone or in-person. The patient will be offered ongoing HIV follow-up care at the site HIV clinic or referred to a clinic of their choice.

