8.3.2 Chemistry

Serum creatinine, sodium, potassium, and ALT, total-bilirubin will be monitored at the local approved site laboratory as part of routine care at the start of CM therapy, initial evaluation for ART, and whenever clinically indicated. Serum aliquots of 0.5-1mL will be frozen at -80°C. An estimated creatinine clearance can be obtained using the Modification of Diet in Renal Disease (MDRD) Study equation:⁶⁵

$$\text{GFR (mL/min/1.73 m}^2\text{)} = 175 \times (\text{Scr}) - 1.154 \times (\text{Age}) - 0.203 \times (0.742 \text{ if female}) \times (1.212 \text{ for African})$$

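### No systematic on-treatment ALT or bilirubin test is scheduled, so unless the synopsis's undefined 'chemistries' include them, the 2-week laboratory endpoint captures liver toxicity only ad hoc

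*Combined protocol and SAP*

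**What the plan says.** **The risk and the monitoring it calls for.** Section 2.3: "Flucytosine can also be associated with severe side effects including hepatotoxicity, bone-marrow depression, and renal toxicity". Section 6.2.2 (Cautions): "Frequent monitoring of hepatic function and of hematopoietic system is indicated during therapy". Treatment is described in 4.1 as "Oral flucytosine (5FC) 60mg/kg/day for 10 days in 3 divided doses", with fluconazole 1200 mg/day through Day 14.

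**The schedule.**
- Section 7.1 marks ALT and total bilirubin twice: at enrollment, and once after induction.
- Section 7.2 lists baseline liver tests as an item separate from the chemistry panel. That panel is sodium, potassium and creatinine at minimum. Baseline samples may be taken within 72 hours either side of enrollment.
- Section 7.3 gives minimum laboratory lists for Day 3, Day 5-7 and Day 10-14. None names a liver test.
- Section 7.4.1 lists at Week 6: "ALT, AST, T-bilirubin, alkaline phosphatase".
- Section 8.3.2 places ALT and bilirubin under Chemistry, to be monitored "as part of routine care at the start of CM therapy, initial evaluation for ART, and whenever clinically indicated".
- The synopsis (Phase II Monitoring) promises CBC, chemistries and kidney function tests three times a week during hospitalized induction. It does not say what chemistries contain.

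**The endpoint.** Section 3.2 has "Incidence of Grade 3-5 abnormal laboratory test results" through Week 2. Section 11.6 makes this the key safety endpoint, and section 11.3 hypothesizes reduced toxicity compared with standard-dose 5-FC.

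**The concern.** The protocol names a severe liver risk and says it needs frequent monitoring on therapy, but the operative schedule has no liver test at any visit in the period when 5-FC is taken and the endpoint is counted. A laboratory endpoint can count only what is sampled. If liver tests are done only when a clinician suspects a problem, asymptomatic rises are the ones most likely to be missed, and a low count partly reflects the lack of testing.

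Two uses of the data are exposed. One is the reduced-toxicity hypothesis in 11.3, if it is read as covering the liver. The other is the hope in 2.6.2 that the results may justify cheaper safety monitoring. In addition, section 11.6 summarizes an analyte as a continuous variable only if its cumulative incidence of laboratory events exceeds 10%. For ALT and bilirubin that trigger would depend on who happened to be tested.

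**Working it through.** The plan states no figure on this point, so there is none to reproduce. The check sets the schedule sections side by side and then computes intervals.

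**1. Scheduled post-baseline tests up to Day 14**

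| Test | Table in 7.1 | Minimum lists in 7.3 |
|---|---|---|
| CBC | 2 (Day 5-7, Day 10-14) | 2 (Day 5-7, Day 10-14) |
| Na, K, creatinine | 2 (Day 5-7, Day 10-14) | 2 (Day 3, Day 10-14) |
| ALT, bilirubin | 0 | 0 |

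Blood counts and creatinine are sampled on treatment under either section; liver tests are not.

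**2. Interval to the next scheduled liver test.** Inputs: 10 days of study 5-FC (4.1); up to 2 earlier days of standard-dose 5-FC allowed (7.2), so the last dose falls at about Day 10 to Day 12; outpatient visit window ±7 days (7.1).
- Week 6 = 6 × 7 = Day 42, window Day 35 to Day 49.
- From a Day 10 last dose: 42 − 10 = 32 days (35 − 10 = 25 to 49 − 10 = 39).
- From a Day 12 last dose: 42 − 12 = 30 days (23 to 37).
- From the end of the endpoint window: 42 − 14 = 28 days, and at the earliest 35 − 14 = 21.
- Read by cell position, the extracted 7.1 table puts the second mark at Week 8 (Day 56): 56 − 10 = 46 days (39 to 53). Sections 7.4.1 and 8.3.1 give Week 6 for the follow-up bloods, so this may be a shift in table extraction.

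**3. What the synopsis could add.** If chemistries include ALT (an assumption), three draws a week give 3 over 7 hospital days and 3 × 10/7 ≈ 4.3 over 10. That would close the gap for inpatients. Against that reading, 7.2 separates liver tests from the chemistry panel, and the three-times-weekly frequency is not carried into 7.1, 7.3 or 8.3. The promise also holds only in hospital. Sections 7.1 and 7.3 allow discharge after Day 7, so a participant discharged then would take 5-FC on Days 8 to 10 (3 days) with no scheduled liver test, even on the generous reading.

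**4. How many events are at issue (illustration only).** The documents give no 2-week Grade 3 or higher hepatic rate on 5-FC. For an assumed rate p among 50 participants, expected cases = 50p and P(at least one) = 1 − (1 − p)^50:
- p = 2%: 1.0 case, 64%
- p = 5%: 2.5 cases, 92%
- p = 10%: 5.0 cases, 99%

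Appendix A gives some context. Among 177 subjects there were 3 Grade 3-5 ALT events (3/177 = 1.7%), 1 bilirubin event (0.6%) and 9 AST events (5.1%). These are events rather than persons, on amphotericin plus fluconazole, with no 2-week limit stated. They do not estimate the rate in this trial.

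**The case against.** **The endpoint is not blind to the liver.** A reader might infer that the 2-week endpoint cannot register hepatic toxicity, or that the schedule would find no cases. The documents do not support that. The lists in 7.3 are minimum lists, 8.3.2 allows liver tests when clinically indicated, and a baseline sample may be drawn up to 72 hours after enrollment. Under 9.7.1 every laboratory value is graded, so any such result inside 2 weeks would count. The defect is unsystematic ascertainment.

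**The synopsis may already provide the tests.** It names chemistries apart from kidney function, and 8.3.2 puts ALT and bilirubin under Chemistry. This is a fair reading, so it would be wrong to say flatly that liver tests occur only at enrollment and Week 6. It is not the only reading, however, and it does not cover treatment days after discharge.

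**The effect on the headline result is small.** The endpoint is any Grade 3-5 laboratory event, and 11.6 notes that such events occur in most of this population. Section 2.6.2 describes the toxicity of high doses as leukopenia, thrombocytopenia and renal injury, and the DOOR ranking grades only hematological laboratory events. All of this stands: the overall incidence would move little. It does not rescue a statement about the liver.

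**Extra tests could unbalance the comparison.** The document history says the schedule was updated to align with the comparator group's. The documents do not give the controls' liver-test schedule, so added sampling in one cohort could make ascertainment unequal. This also stands, and it limits how added data may be used.

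**Conclusion.** The concern holds in limited form. Sections 2.3 and 6.2.2 do not agree with 7.1, 7.3 and 8.3.2: there are no systematic ALT or bilirubin tests between baseline and Day 14, against two each for CBC and for sodium, potassium and creatinine. The next scheduled test comes about 32 days after a Day 10 last dose (25 to 39), taking Week 6 as the visit meant. Unless the synopsis's chemistries include ALT, hepatic events reach the key safety endpoint only through ad hoc or late-baseline tests. A low hepatic count could then not support the reduced-toxicity hypothesis for the liver.

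The count of zero rests on the schedule and visit sections; it changes for inpatients if chemistries are defined to include ALT. The hematological and renal components, and the primary endpoint, are not affected. The event rates in the illustration are assumed.

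Magnesium is a separate, secondary point. Sections 2.6.1 and 6.2.1.1 describe hypomagnesemia as a common, life-threatening risk of IV amphotericin and ask for magnesium monitoring, but no schedule or panel lists it. The manual of operations, which was not available, may cover its clinical management.

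**What to change.** 1. Reconcile the synopsis (Phase II Monitoring), 6.2.2, 7.1, 7.2, 7.3, 7.4.1 and 8.3.2, including the Week 6 or Week 8 placement, and define what chemistries contain. Which monitoring frequency is clinically right is for the sponsor to decide.
2. For endpoint ascertainment, ALT and total bilirubin could be run on blood already collected at Day 5-7 and Day 10-14 and added to 7.1, 7.3 and 8.3.2. The cost is a protocol amendment and at most 2 assays × 2 visits × 50 participants = 200 assays, with no extra visit or draw. Because the controls' sampling is not documented, restrict any comparison of hepatic events to comparable sampling times or report them descriptively.
3. If the present schedule is kept, state in 11.6 and in the report that the 2-week laboratory endpoint and any reduced-toxicity conclusion do not cover hepatic events. This costs a sentence.
4. Separately, reconcile 2.6.1 and 6.2.1.1 with the schedule and panels on magnesium.
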